## Post-authorisation Safety Study (PASS) Information

Title	Observational Post-Marketing Safety Study of Ixekizumab and Other Systemic and Non-Systemic Treatments for Paediatric Psoriasis
Study Identifier	IIF-MC-B015
Version identifier	Version: 1.0
Date of last version	NA
EU PAS Register No:	EUPAS36306
Active substance	L04AC13 Ixekizumab
Medicinal product(s):	Ixekizumab
Product reference:	Taltz, MA numbers EU/1/15/1085/001-006
Procedure number:	EMA/H/C/003943/II/0031
Marketing authorisation holder(s)	Eli Lilly and Company
Joint PASS	No
Research question and objectives	
The objectives of this study are to monitor the uptake of ixekizumab in a real-world paediatric psoriasis population, to characterise the demographic and clinical characteristics of paediatric patients receiving ixekizumab and appropriate comparator medications, and to obtain information about the long-term safety pertaining to serious infections and inflammatory bowel disease. Once target study size is reached, an additional objective is to compare the incidence of serious infections and IBD in children exposed to ixekizumab to:
 
 
(1) Children with plaque psoriasis who were treated with another biologic approved for paediatric use
 
(2) Children with plaque psoriasis who were treated with systemic non-biologic treatments
 
(3) Children with plaque psoriasis who were treated only with non-systemic treatments.
 
 
The null hypothesis is that incidence of SI and IBD are similar in paediatric psoriasis patients exposed to ixekizumab when compared to paediatric populations unexposed to ixekizumab.

Country(ies) of study	United States
Author	
PPD Principal Investigator PPD, HealthCore Inc. [name], United States Email: PPD
 
PPD Principal Scientist PPD, HealthCore, Inc. [name], United States Email: PPD

## 1. List of Abbreviations

Term	Definition
AE	Adverse event
CD	Crohn's disease
CI	Confidence interval
EMA	European Medicines Agency
ENCePP	European Network of Centres for Pharmacoepidemiology and Pharmacovigilance
ERB	Ethical review board
EU PAS	European Union Post-authorisation Studies
FDA	Food and Drug Administration
GPI	Generic Product Identifier
HCPCS	Healthcare Common Procedure Coding System
HIRD	HealthCore Integrated Research Database
IBD	Inflammatory bowel disease
ICD-9	International Classification of Diseases, Ninth Revision
ICD-10	International Classification of Diseases, Tenth Revision
IR	Incidence rate
IRR	Incidence rate ratio
MRP	Medical Record Plan
NDC	National Drug Code
PASS	Post-authorisation safety study
PS	Propensity score
PHI	Protected health information

PPV	Positive predictive value
PRAC	Pharmacovigilance Risk Assessment Committee
SAP	Statistical analysis plan
SI	Serious infection
UC	Ulcerative colitis
US	United States

---

## 4. Abstract

### Title

Observational Post-Marketing Safety Study of Ixekizumab for the Treatment of Paediatric Psoriasis

Version: 1.0

Main Author: PPD

### Rationale and background:

Ixekizumab is a humanised IgG4 monoclonal antibody that binds with the IL-17A cytokine. The paediatric dosage is administered once monthly as a subcutaneous injection, depending on the child's weight. Ixekizumab received approval from the Food and Drug Administration (FDA) in March of 2020 and the EMA in June 2020 for paediatric patients aged 6 to less than 18 years of age with moderate-to-severe plaque psoriasis who are candidates for systemic treatment and phototherapy. The European Medicines Agency's (EMA) Pharmacovigilance Risk Assessment Committee (PRAC) has requested a new study to evaluate the long-term safety study of ixekizumab in paediatric patients with psoriasis.

### Research question and objectives

The objectives of this study are to monitor the exposure to ixekizumab among children 6 to less than 18 years of age with plaque psoriasis and to measure the incidence of serious infections (SI) and flares of both new onset and prevalent inflammatory bowel disease (IBD) (Crohn's disease (CD) and ulcerative colitis (UC)) among children exposed to ixekizumab. Once target study size is reached, an additional objective is to compare the incidence of serious infections and IBD in children exposed to ixekizumab to children with plaque psoriasis who were treated with (1) another biologic approved for paediatric use and (2) systemic non-biologic treatments and (3) only non-systemic treatments.

The null hypothesis is that incidence of SI and IBD are similar in paediatric psoriasis patients exposed to ixekizumab when compared to paediatric populations unexposed to ixekizumab.

### Study design

We are proposing a two-phased approach where Phase 1 includes product uptake monitoring to achieve sufficient patient accrual. Once the target number of patients are accrued during Phase 1, Phase 2 will include a cohort study with comparative analyses of the incidence of safety outcomes among children with plaque psoriasis who have exposure to ixekizumab relative to three comparator groups.

### Population

This study will include children newly exposed to ixekizumab or comparator medications as identified through pharmacy and medical claims in the HealthCore Integrated Research Database (HIRD). The three comparator groups are (1) children 6-<18 years of age treated with etanercept, which is approved for paediatric patients with moderate-to-severe plaque psoriasis; (2) children 6-<18 years of age who were treated with systemic non-biologic medications such as acitretin, cyclosporine, and methotrexate; (3) children 6-<18 years of age treated only with non-systemic treatments such as topical corticosteroids and calcipotriene.

Across the cohorts, children will be required to have a minimum of six months baseline eligibility prior to a dispensing of the study drug.

### **Variables**

In Phase 1, exposure to ixekizumab or comparators will be ascertained from claims based on the National Drug Code (NDC) or Generic Product Identifier (GPI) for outpatient pharmacy dispensing and Healthcare Common Procedure Coding System (HCPCS) codes for infusions that occur in a healthcare setting. Defining exposure episodes for the primary and sensitivity analyses will depend on use of these medications in routine clinical practice. Therefore, preliminary work evaluating drug utilisation will be conducted before finalising exposure episodes. Outcomes and covariates, including demographics, clinical characteristics, healthcare utilisation, and medication use will be ascertained using administrative claims. Additionally, in Phase 1, outcomes will be validated by medical record review.

### **Data sources**

This study will be conducted using the HIRD, a longitudinal medical and pharmacy claims database from health plan members across the United States (US). Depending on accrual of exposed children, additional data sources may be added during Phase 1 (uptake monitoring). All available data prior to the dispensing of ixekizumab or comparators will be used to assess baseline characteristics. Claims will be utilised as the data source for exposure status, endpoints, and covariates. Medical records will be utilised to validate endpoints as necessary.

### **Study size**

The available number of exposed children will depend on the uptake of ixekizumab in the US among children between the ages of 6 to <18. With 392 ixekizumab-treated children and 392 etanercept-treated children, the study will achieve 80% power to detect a 16.8-fold difference in the incidence of SI and a 3.9-fold difference in the incidence in new onset or exacerbations of IBD between ixekizumab and etanercept. Additionally, with 2,352 children prescribed systemic non-biologic treatments and 3,528 children prescribed only non-systemic treatments, the study will achieve 80% power with to detect at least an 8.9-fold difference in the incidence of SI and IBD between ixekizumab and systemic non-biologic treatment or non-systemic treatment. If we are not on track to accrue the targeted number of patients for an interim analysis by second quarter of 2023, we will reach out to additional data sources to determine the number of ixekizumab-exposed children that could be identified by expanding the study to include multiple databases, or consider extending the timeline of the study. Feasibility of continuing the study, either as a single database or a multi-database study, will be considered in consultation with regulatory authorities.

### **Data analysis**

- In Phase 1, the number of children exposed to ixekizumab or comparator medications, duration of exposure, and total outcomes will be identified and validated.
- In Phase 2, we will describe children who were exposed either to ixekizumab, a biologic comparator (etanercept), non-biologic comparator, or only non-systemic comparators, with respect to demographic, clinical, treatment, and utilisation characteristics.

- We will use exposure propensity scores to match comparators to the ixekizumab cohort. Covariate balance will be assessed using absolute standardised differences with a target value of less than 0.1 [1].
- For each outcome, the incidence of SI and flares of existing or new IBD will be presented for each exposure group. Incidence rate ratios (IRR) and their corresponding 95% confidence intervals (CI) will be calculated comparing ixekizumab-exposed children to children exposed to etanercept, non-biologic medications, and non-systemic medications. Effect estimates will be stratified by duration of exposure, age, and gender.

### **Milestones**

Upon approval of the protocol and statistical analysis plan (SAP), data collection will begin by 31 August 2021 using data that spans from March of 2020 through October 2025. Annual product uptake monitoring in Phase 1 will monitor ixekizumab and comparator drug uptake to determine feasibility and optimal timing for initiation of cohort surveillance (Phase 2). Uptake monitoring may suggest the need to incorporate additional data sources, extend the time period for uptake monitoring, or both. The Final Study Report is expected to be completed by 30 April 2026.

## 5. Amendments and Updates

Not applicable at this time.

## 6. Milestones

Milestone	Planned date
Start of data collection	31 August 2021
Interim report of study results	30 June 2023 a
End of data collection	30 October 2025
Final report of study results	30 April 2026

a Interim analysis will be performed once one-third of targeted ixekizumab exposures have accrued. If a sufficient number of exposures have not accrued for an interim analysis by June 2023, we will reach out to additional data sources to determine the number of ixekizumab-exposed children that could be identified by expanding the study to include multiple databases. Feasibility of continuing the study, either as a single database or a multi-database study, will be considered in consultation with regulatory authorities.

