## 9.8. Study Size

The available number of exposed children will depend on the uptake of ixekizumab in the US among children between the ages of 6-<18 years. Preliminary feasibility counts from the HIRD indicate that biologic medications (etanercept and ustekinumab) are not widely used in paediatric psoriasis populations. Over a four-year period (2015-2019), there were approximately 580 paediatric psoriasis patients treated with a biologic, which, if divided equally among two available medications with steady accrual over 4 years would correspond to ~70 ((580/4 years)/2 medications) patients per medication, per year. No requirements for continuous health plan eligibility or other inclusion criteria were made in obtaining these preliminary counts. Although there remains a significant unmet medical need in this population, the uptake of a single medication such as ixekizumab is expected to occur more slowly than previously available biologic treatments and be impacted by the introduction of new medications to the marketplace. Available sample size will also be reduced by the requirement for continuous health plan eligibility, which is needed to assess baseline patient characteristics. Additionally, preliminary feasibility counts from the HIRD (2015-2019) indicate that non-biologic (N=2,551) and non-systemic medications (N>4,000) are more commonly prescribed in the paediatric population, allowing us to increase the ratio of comparator to ixekizumab for those two analyses. No requirements for continuous health plan eligibility or other inclusion criteria were made in obtaining these preliminary counts.

Assuming approximately 70 ixekizumab-exposed patients per year, this study will identify approximately 392 ixekizumab-exposed children from the time of the FDA paediatric indication approval (March 30, 2020) through the end of data collection (October 30, 2025). The lowest detectable relative risks with 80% power given a 1:1 etanercept:ixekizumab ratio for the study outcomes to be analyzed are described in Table 1. Table 1 also displays the lowest detectable relative risk with 80% power for estimated sample sizes given a 6:1 non-biologic comparator: ixekizumab and 9:1 non-systemic comparator: ixekizumab ratio for each of the study outcomes. All calculations assume a two-sided Type I error rate of 0.05 and baseline rates of serious infection and IBD in a paediatric population from the published literature [14, 15].

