## 9.10. Data Analysis

### 9.10.1. Primary Analysis

In Phase 1, the number of children with exposure to ixekizumab, comparator drugs, and incidence of SI and IBD will be calculated. All cases of SI and IBD will be submitted for medical adjudication by clinical specialists and results of the validation will be presented in the interim and final reports. In order to achieve our target size by October 2025, we will assess uptake of the ixekizumab and comparator drugs at the end of second quarter of 2023 and determine if additional data sources need to be incorporated into the study or if the timeline for uptake monitoring needs to be extended. No additional analysis is planned for Phase 1.

In Phase 2, we will describe the number and percentage of children in each cohort for all of the demographic, clinical, treatment, and utilisation characteristics described in Section 9.6.3. Applicable baseline characteristics will then be used to calculate an exposure propensity score (PS) by modelling the probability of ixekizumab exposure versus the etanercept, non-biologic drugs, and non-systemic drugs (separately) as a function of the covariates [17]. Propensity score

matching will be used to balance risk factors for SI or IBD among ixekizumab-treated patients and each of the comparison groups. We will create separate propensity scores for SI and IBD as the risk factors for these outcomes are different. Propensity score matching uses variables identified as potential risk factors in the baseline period before the first dispensing of the drug of interest (e.g., age, geographic region, current comorbidities, and calendar time) as predictors of the choice of therapy. Propensity score matching produces groups that have similar distributions of variables included in the PS as well as any variables strongly associated with these covariates.

For each outcome (Section 9.6.2), we will describe the IR (calculated as the number of events divided by the person-time at risk). Incidence rate ratios (IRR) and corresponding 95% CIs will be calculated comparing children exposed to ixekizumab to children exposed to etanercept, children treated with non-biologic prescription medications, and children treated with topicals.

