Another limitation of this study is the use of non-systemic topical treatments as a comparator group for a biologic medication indicated for children with moderate-to-severe paediatric plaque psoriasis. Patients prescribed non-systemic topical medication might be expected to have a milder form of the disease or not be appropriate candidates for biologic medications due to other comorbidities. Thus, we expect reduced comparability between the children in the ixekizumab and non-systemic topicals groups. Any differences in disease severity and indications for the non-systemic topicals between treatment groups introduces potential confounding bias that must be considered when interpreting the results of this study.

The main limitations relate to uncertainties regarding the numbers of subjects available to study for a new medication, and limitations inherent in database studies, including accuracy of codes used to identify outcomes. Also, uptake of a new product (plus the follow-up time necessary to observe events) will determine the time at which a sufficient study size for analysis will be accrued in the database, as discussed in Section 9.8. Additionally, the sample size for this study was calculated based on the number of children in the HIRD (between 2015-2019) with moderate-to-severe plaque psoriasis who were prescribed biologic medications. Given the rare occurrence of moderate-to-severe paediatric plaque psoriasis requiring biologic medications, this study is planned for a sample size to detect a 16.8-fold difference in risk of IBD among children

prescribed ixekizumab versus etanercept. However, among children who were prescribed non-biologics as compared to those prescribed ixekizumab, the study will have the sample size to detect  $\geq 8.9$ -fold increase in risk for IBD. Furthermore, because SI is more prevalent than IBD, the planned sample size will allow us to detect a  $\geq 3.9$ -fold difference in risk for SI among children who were prescribed ixekizumab, compared to those who were prescribed etanercept.

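### Accrual target, interim trigger, mid-2023 check and Phase 2 gate count children only, so meeting them does not establish the person-time assumed in Table 1

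*Protocol*

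**What the plan says.** **Decision rules, all in children or exposures.**
- Abstract, Study design: "Once the target number of patients are accrued during Phase 1, Phase 2 will include a cohort study". Section 9.3 makes the comparative analysis conditional on enough exposures being identified.
- Section 6, footnote a: "Interim analysis will be performed once one-third of targeted ixekizumab exposures have accrued". If too few have accrued by June 2023, the sponsor will approach other data sources to "determine the number of ixekizumab-exposed children that could be identified by expanding the study to include multiple databases".
- Sections 9.7, 9.8 and 9.10.1 rest the decision to add data sources or extend the timeline on uptake and sample size.
- Section 9.8 sets the target: "Assuming approximately 70 ixekizumab-exposed patients per year, this study will identify approximately 392 ixekizumab-exposed children", counted "from the time of the FDA paediatric indication approval (March 30, 2020) through the end of data collection (October 30, 2025").

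**Analysis, in person-time.** Section 9.10.1: "we will describe the IR (calculated as the number of events divided by the person-time at risk"). Section 9.6.1 provisionally ends exposed time five half-lives after the last dispensing or administration and removes longer gaps.

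**Follow-up.** Section 9.12 says that "uptake of a new product (plus the follow-up time necessary to observe events) will determine the time" at which study size is sufficient, and refers to Section 9.8 for the discussion. Section 9.8 discusses uptake and baseline eligibility but not follow-up time after entry. Table 1 applies five-year background risks (1% for serious infection, 0.1% for IBD) to the full cohort sizes.

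**The concern.** A child with one dispensing and a child treated for several years count the same towards every target and trigger, but contribute very different amounts to an incidence rate. Entry is staggered over the whole study period, so person-time trails well behind the child count. The study can therefore be exactly on plan by its own rules and still hold much less exposure than its stated detectable relative risks require.

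The point at risk is the mid-2023 decision on extending the timeline or adding databases, and after it the decision to start Phase 2. With 58% of the children in hand the study may be read as on track, with no figure in the protocol to show how much exposure, or how many expected events, that represents.

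**Working it through.** **Inputs.** 70 ixekizumab children per year, 392 in total, entry window 30 March 2020 to 30 October 2025 (Section 9.8). One-third trigger (Section 6). Check at the end of the second quarter of 2023 (Section 9.10.1). Background risk over five years 1% (serious infection) and 0.1% (IBD), 80% power, ratios 1:1, 6:1 and 9:1 (Section 9.8 and Table 1). "All calculations assume a two-sided Type I error rate of 0.05".

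**Step 1: reproduce Table 1.** Use the conditional binomial form of a Poisson comparison. With k comparator children per ixekizumab child, five-year risk p and relative risk RR:
- ixekizumab events E1 = 392 x p x RR; comparator events E0 = k x 392 x p; E = E1 + E0
- null share q0 = 1/(1 + k); alternative share q1 = E1/E
- solve [(q1 - q0) x sqrt(E) - 1.96 x sqrt(q0(1 - q0))] / sqrt(q1(1 - q1)) = 0.84

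Example, serious infection 1:1 at RR 3.97: E0 = 3.92, E1 = 15.56, E = 19.48, q1 = 0.799. The left side is 0.845, as required.

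| Ratio | SI, Table 1 | SI, reproduced | IBD, Table 1 | IBD, reproduced |
|---|---|---|---|---|
| 1:1 | 3.94 | 3.97 | 16.8 | 16.83 |
| 6:1 | 2.9 | 2.90 | 8.9 | 8.90 |
| 9:1 | 2.82 | 2.83 | 8.5 | 8.48 |

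All six cells agree within 1%. The other usual formulas tried (pooled and unpooled two-proportion, continuity-corrected, log relative risk) do not reproduce all six. Table 1 therefore gives every child the whole five-year risk: 392 x 5 = 1,960 ixekizumab child-years.

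**Step 2: person-time that staggered entry allows.** With steady entry at 70 per year and nobody stopping, children = 70t and child-years = 70t²/2. The annual background rates are 1%/5 = 0.2% and 0.1%/5 = 0.02%.

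| Date | t (years) | Children | Child-years, at most | Share of 1,960 | Expected background SI / IBD |
|---|---|---|---|---|---|
| 30 June 2023, on plan | 3.25 | 227 (58% of 392) | 370 | 19% | 0.74 / 0.074 |
| 30 June 2023, one-third trigger only just met | 3.25 | 131 (33%) | 131 x 3.25/2 = 213 | 11% | 0.43 / 0.043 |
| 30 October 2025, on plan | 5.585 | 391 (stated as 392) | 1,092 | 56% | 2.18 / 0.22 |

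**Step 3: detectable relative risk at the ceiling.** Use the formula of step 1 with 1,092 child-years in place of 1,960, and assume that comparator children have the same person-time per child. Check for serious infection 1:1 at RR 5.4: E0 = 1,092 x 0.002 = 2.18, E1 = 11.79, q1 = 0.844; the left side is 0.841.

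| Ratio | SI: Table 1 -> at ceiling | IBD: Table 1 -> at ceiling |
|---|---|---|
| 1:1 | 3.94 -> 5.4 | 16.8 -> 26.5 |
| 6:1 | 2.9 -> 3.7 | 8.9 -> 12.6 |
| 9:1 | 2.82 -> 3.6 | 8.5 -> 11.9 |

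**Step 4: effect of stopping (assumed, not in the documents).** With exponential time on drug of mean m, child-years = 70 x [m x t - m²(1 - exp(-t/m))]. For m of 1, 2 and 3 years, October 2025 gives about 321, 519 and 641 child-years (16%, 26% and 33% of 1,960). The child count is the same in all three cases.

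**The case against.** **The information will be there.** A reader might infer that the feasibility check cannot show whether the study is informative. The documents do not support that. Phase 1 identifies duration of exposure and outcomes (Abstract, Data analysis), and annual reports give incidence rates, which need person-time (Section 9.2). Section 9.3 ties informativeness to outcomes as well as patients, and continuation is to be discussed with regulators. This stands: only a criterion is missing.

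**The lowest information fraction is not at the decision.** One-third of the children could be reached in 131/70 = 1.87 years, about February 2022, with 131 x 1.87/2, about 123 child-years (6% of 1,960). It is tempting to lead with that figure, but no decision to extend or add databases is scheduled then. At mid-2023 the range is about 11% to 19%. The interim report is also descriptive, with no comparative test attached. This stands.

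**Against plan, both units can give the same signal.** With steady entry and no stopping, 131 of 227 children is 58% and 213 of 370 child-years is also 58%. This stands for that idealised case. The units separate once children stop treatment (step 4) or entry is back-loaded, and neither would show in a count.

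**Part of the gap belongs to Table 1.** It credits five years to every child, while staggered entry allows a mean of at most about 2.8. Against the attainable 1,092, mid-2023 on plan is 370/1,092 = 34%. This stands, and it is why 1,960 is the wrong yardstick for progress: the study would fall short of it even with perfect accrual.

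**Comparator person-time.** A reader might infer that the 9:1 topical ratio shrinks in person-time because topical episodes are short. The protocol gives no topical episode length and leaves episode definitions to drug-utilisation work and the SAP, so no figure can be put on this.

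**Conclusion.** The point holds as a gap between the unit of the decision rules and the unit of the analysis. Meeting the child counts, even exactly on schedule, does not establish the exposure behind Table 1: at most 19% of it at mid-2023 and at most 56% at the end of data collection.

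These shares rest on the protocol's 70 per year, steady entry from 30 March 2020 and no discontinuation. For the planned uptake they are ceilings, and any stopping lowers them. The relative risks at the ceiling further assume equal person-time per child in the comparator groups and the background risks of Table 1.

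This is not a detail that can wait for the SAP, because the trigger, the gate and the criterion for adding data sources are fixed in the protocol. It does not make the study uninformative or the interim report misleading. It is a cheap improvement.

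**What to change.** 1. In Sections 6 and 9.8, keep the child counts and add a criterion in on-treatment person-years and expected events per arm. Apply it to the mid-2023 decision to extend or add databases and to the Phase 2 gate, and align Section 9.3 and the Abstract.
2. Benchmark the criterion to attainable person-years: a ceiling of about 370 at 30 June 2023 and 1,092 at 30 October 2025 for ixekizumab, lowered by a stated discontinuation assumption. Without that adjustment, observed on-treatment time would lag the benchmark by construction. Do not use 1,960 as the yardstick.
3. Restate Table 1, and the detectable differences repeated in the Abstract and Section 9.12, for those person-years. The step 3 values are the most favourable case at the planned uptake.
4. Put into Section 9.8 the discussion of follow-up time to which Section 9.12 refers.

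The cost is protocol wording, a recalculated table and one more column in the annual uptake report, since duration of exposure is already collected. The downside is that progress and detectable relative risks will look less favourable than they do now.
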